7.2. Participant Discontinuation/Withdrawal From the Study

A participant may withdraw from the study at any time at his/her own request. Reasons for discontinuation from the study include the following:

- Refused further follow-up;
- Lost to follow-up;
- Death;
- Study terminated by sponsor;

At the time of discontinuing from the study, if possible, an early discontinuation visit should be conducted. See the [SOA](#) for assessments to be collected at the time of study discontinuation and follow-up and for any further evaluations that need to be completed.

The early discontinuation visit applies only to participants who are enrolled/randomized and then are prematurely withdrawn from the study. Participants should be questioned regarding their reason for withdrawal.

The participant will be permanently discontinued both from the study intervention and from the study at that time.

If a participant withdraws from the study, he/she may request destruction of any remaining samples taken and not tested, and the investigator must document any such requests in the site study records and notify the sponsor accordingly.

If the participant withdraws from the study and also withdraws consent (see Section 7.2.1) for disclosure of future information, no further evaluations should be performed and no additional data should be collected. The sponsor may retain and continue to use any data collected before such withdrawal of consent.

Lack of completion of all or any of the withdrawal/early termination procedures will not be viewed as protocol deviations so long as the participant's safety was preserved.

7.2.1. Withdrawal of Consent

Participants who request to discontinue receipt of study intervention will remain in the study and must continue to be followed for protocol-specified follow-up procedures. The only exception to this is when a participant specifically withdraws consent for any further contact with him or her or persons previously authorized by the participant to provide this information. Participants should notify the investigator in writing of the decision to withdraw consent from future follow-up, whenever possible. The withdrawal of consent should be explained in detail in the medical records by the investigator, as to whether the withdrawal is only from further receipt of study intervention or also from study procedures and/or posttreatment study follow-up, and entered on the appropriate CRF page. In the event that vital status (whether the participant is alive or dead) is being measured, publicly available information should be used to determine vital status only as appropriately directed in accordance with local law.

7.3. Lost to Follow up

A participant will be considered lost to follow-up if he or she repeatedly fails to return for scheduled visits and is unable to be contacted by the study site.

The following actions must be taken if a participant fails to return to the clinic for a required study visit:

- The site must attempt to contact the participant and reschedule the missed visit as soon as possible and counsel the participant on the importance of maintaining the assigned visit schedule and ascertain whether or not the participant wishes to and/or should continue in the study;
- Before a participant is deemed lost to follow-up, the investigator or designee must make every effort to regain contact with the participant (where possible, 3 telephone calls and, if necessary, a certified letter to the participant's last known mailing address or local equivalent methods). These contact attempts should be documented in the participant's medical record;
- Should the participant continue to be unreachable, he/she will be considered to have withdrawn from the study.

8. STUDY ASSESSMENTS AND PROCEDURES

The investigator (or an appropriate delegate at the investigator site) must obtain a signed and dated ICD before performing any study-specific procedures.

Study procedures and their timing are summarized in the [SOA](#). Protocol waivers or exemptions are not allowed.

Safety issues should be discussed with the sponsor immediately upon occurrence or awareness to determine whether the participant should continue or discontinue study intervention.

Adherence to the study design requirements, including those specified in the [SOA](#), is essential and required for study conduct.

All screening evaluations must be completed and reviewed to confirm that potential participants meet all eligibility criteria. The investigator will maintain a screening log to record details of all participants screened and to confirm eligibility or record reasons for screening failure, as applicable.

Participants will be screened within 28 days prior to administration of the study intervention to confirm that they meet the study population criteria for the study. If the time between screening and dosing exceeds 28 days as a result of unexpected delays (eg, delayed drug shipment), then participants do not require rescreening if the laboratory results obtained prior to first dose administration meet eligibility criteria.

Every effort should be made to ensure that protocol-required tests and procedures are completed as described. However, it is anticipated that from time to time there may be circumstances outside the control of the investigator that may make it unfeasible to perform the test. In these cases, the investigator must take all steps necessary to ensure the safety and well-being of the participant. When a protocol-required test cannot be performed, the investigator will document the reason for the missed test and any corrective and preventive actions that he or she has taken to ensure that required processes are adhered to as soon as possible. The study team must be informed of these incidents in a timely manner.

For samples being collected and shipped, detailed collection, processing, storage, and shipment instructions and contact information will be provided to the investigator site prior to initiation of the study.

The total blood sampling volume for individual participants in this study is approximately 450 mL. The actual collection times of blood sampling may change. Additional blood samples may be taken for safety assessments at times specified by Pfizer, provided the total volume taken during the study does not exceed 550 mL during any period of 60 consecutive days.

To prepare for study participation, participants will be instructed on the information in the Lifestyle Considerations and Concomitant Therapy sections of the protocol.

8.1. Efficacy Assessments

Efficacy assessments are not evaluated in this study.

8.2. Safety Assessments

Planned time points for all safety assessments are provided in the **SOA**. Unscheduled clinical laboratory measurements may be obtained at any time during the study to assess any perceived safety issues.

8.2.1. Physical Examinations

A physical examination will include, at a minimum, head, ears, eyes, nose, mouth, skin, heart and lung examinations, lymph nodes, and gastrointestinal, musculoskeletal, and neurological systems.

Physical examinations must be conducted by a physician.

Height will be measured at screening only.

Investigators should pay special attention to clinical signs related to previous serious illnesses.

CCI

8.2.3. Vital Signs

Supine BP will be measured with the participant's arm supported at the level of the heart, and recorded to the nearest mm Hg after approximately 5 minutes of rest. The same arm (preferably

the dominant arm) will be used throughout the study. Participants should be instructed not to speak during measurements. When a meal or snack is scheduled at the same time as measuring BP and PR, the measuring BP and PR must be performed prior to the meal/snack. When triplicate BP and PR are required, they will be obtained approximately 2 to 4 minutes apart; the average of the triplicate BP and PR measurements collected at each nominal time point on Day -1 will serve as each participant's time-controlled baseline values.

The same properly sized and calibrated BP cuff will be used to measure BP each time. The use of an automated device for measuring BP and pulse rate is acceptable; however, when done manually, pulse rate will be measured in the brachial/radial artery for at least 30 seconds. When the timing of these measurements coincides with a blood collection, BP and pulse rate should be obtained prior to the nominal time of the blood collection.

Additional collection times, or changes to collection times, of BP and pulse rate will be permitted, as necessary, to ensure appropriate collection of safety data.

8.2.4. Electrocardiograms

Standard 12-lead ECGs should be collected at times specified in the [SOA](#) section of this protocol using an ECG machine that automatically calculates the heart rate and measures PR, QT, and QTcF intervals and QRS complex. All scheduled ECGs should be performed after the participant has rested quietly for at least 10 minutes in a supine position. When a meal or snack is scheduled at the same time as an ECG, the ECG must be performed prior to the meal/snack.

Triplicate 12-lead ECGs will be obtained approximately 2 to 4 minutes apart; the average of the triplicate ECG measurements collected at each nominal time point on Day -1 will serve as each participant's time-controlled baseline QTcF value.

To ensure safety of the participants, a qualified individual at the investigator site will make comparisons to baseline measurements.

If a) a postdose QTcF interval remains ≥ 30 msec from the baseline **and** is > 450 msec; or b) an absolute QTcF value is ≥ 500 msec for any scheduled ECG for greater than 4 hours (or sooner, at the discretion of the investigator); or c) QTcF intervals get progressively longer, the participant should undergo continuous ECG monitoring. A cardiologist should be consulted if QTcF intervals do not return to less than the criterion listed above after 8 hours of monitoring (or sooner, at the discretion of the investigator).

In some cases, it may be appropriate to repeat abnormal ECGs to rule out improper lead placement as contributing to the ECG abnormality. It is important that leads be placed in the same positions each time in order to achieve precise ECG recordings. If a machine-read QTcF value is prolonged, as defined above, repeat measurements may not be necessary if a qualified medical provider's interpretation determines that the QTcF values are in the acceptable range.

ECG values of potential clinical concern are listed in [Appendix 7](#).

8.2.5. Management of Glycemic Control

HAEs and FPG will be routinely monitored during participation in the study.

Based on this information, as well as review of the results reported by the central laboratory, an assessment of any symptomatic and asymptomatic occurrence of hypo- or hyper-glycemia must be undertaken.

8.2.5.1. Home Glucose Monitoring

- To aide in management of their T2DM, all participants will be provided home glucose monitoring supplies including a glucometer, instructions on the use of the glucometer and accompanying supplies.
- Home glucose monitoring logs will be provided to participants for completion at home and brought to each visit to the site along with the glucometers. Investigators must review the home glucose monitoring logs completed by the participants and the readings stored in the glucometer device at all time points listed in the [SOA](#).
- Participants must perform home glucose monitoring at least 3 times weekly following at least an 8-(preferably 10-) hour fast (except water). However, the investigator may recommend daily home glucose monitoring if needed.
- Less frequent glucose monitoring will NOT be considered a protocol deviation unless the participant fails to monitor his/her glucose for 3 or more consecutive days.
- If the participant experiences symptoms of hypoglycemia, home glucose monitoring should be performed, and these symptoms, along with the glucometer measurement, should be captured on the home glucose monitoring log.
- If the participant uses his/her own glucometer, and not one provided by the Sponsor, a protocol deviation will NOT be recorded provided the investigator is still able to monitor the participant's daily glucose values according to the criteria stated above.

8.2.5.2. Management of Hypoglycemia

GLP-1R agonists typically are not associated with hypoglycemia unless co-administered with anti-diabetic agents that can cause hypoglycemia (such as insulin or sulfonylureas), which are prohibited in this study. Blood glucose concentrations will be monitored throughout the study via glucometer, and monitoring of symptomatic hypoglycemic AEs will be performed. In addition, all participants will be instructed on Day -2 regarding the symptoms associated with, and management of, hypoglycemia, which will permit the monitoring of symptomatic HAEs.

Any episode of hypoglycemia must be captured on the Adverse Event Form CRF with specific details captured on the Hypoglycemic Event Details CRF. For the definition of a hypoglycemic episode and severity categorization see [Section 8.2.5.2.1](#) below.

Participants noted to have a fasting glucose value (during home glucose monitoring) meeting the definition of hypoglycemia must be instructed to repeat the measurement the next day (following at least an 8 [preferably 10] hour fast, except water). If the second measurement also meets the below definition, participants must be asked to return to the site within 1 to 3 days (following at least an 8 [preferably 10] hour fast, except water) and have blood collected and sent to the central laboratory for analysis of FPG.

8.2.5.2.1. Definition and Severity of Categorization of Hypoglycemic Adverse Event (HAE)

Based on review of the participant completed home glucose monitoring log at each time point specified in the **SOA**, as well as results reported by the central laboratory, the investigator must assess the glucose values as well as any symptoms documented.

HAE is defined as **one** of the following: ¹⁵

1. **Asymptomatic hypoglycemia:** An event *not* accompanied by typical symptoms of HAE but a glucose value of <70 mg/dL (3.9 mmol/L) using either glucometer (FSBG) or sponsor-identified central laboratory (plasma glucose);
2. **Documented symptomatic hypoglycemia:** An event during which typical symptoms of HAE are accompanied *with* a glucose value of <70 mg/dL (3.9 mmol/L) using glucometer (or sponsor-identified central laboratory) **and** the clinical picture includes prompt resolution with food intake, subcutaneous glucagon, or glucose administration;
3. **Probable symptomatic hypoglycemia:** An event during which symptoms of HAE are *not* accompanied by a glucose determination but was presumably caused by a glucose concentration of <70 mg/dL (3.9 mmol/L), **and** the clinical picture includes prompt resolution with food intake, subcutaneous glucagon, or glucose administration.

Each episode of HAE must be categorized with respect to severity. In order to characterize the event as severe, **all three (3) criteria** below must be met:

1. The participant was unable to treat himself/herself. Neurologic impairment, and not the age of the participant, is the explanation for why the participant could not treat himself/herself and required the assistance of another person.
2. The participant exhibited at least one of the following neurological symptoms:
 - Memory loss;
 - Confusion;
 - Uncontrolled behavior;
 - Irrational behavior;
 - Unusual difficulty in awakening;

- Suspected seizure;
- Seizure;
- Loss of consciousness.

3. Either:

- If blood glucose was measured and was ≤ 54 mg/dL (2.7 mmol/L) using glucometer (or central laboratory); or
- If blood glucose was not measured, the clinical manifestations were reversed by oral carbohydrates, subcutaneous glucagon, or glucose administration.

Events that do not meet all the criteria above for severe HAE are characterized as mild or moderate in severity.

Any episode of HAE must be captured on the HAE CRF.

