2.3.1. Risk Assessment

Potential Risk of Clinical Significance	Summary of Data/Rationale for Risk	Mitigation Strategy
Study Intervention(s) PF-06882961		
Thyroid C-cell tumors	
The potential risks are based on product labeling for injectable GLP-1R agonists (ie, liraglutide, dulaglutide, and exenatide) due to dose-dependent and treatment duration-dependent thyroid C-cell tumors in nonclinical studies in rats and mice at clinically relevant exposures.
 
Thyroid C-cell tumors have not been observed with PF-06882961 in clinical or nonclinical studies.
	Potential participants with a personal or family history of medullary thyroid carcinoma or MEN2 are excluded from the clinical development program. Thyroid function tests are included in the clinical trial protocols to monitor participants' thyroid function.
Pancreatitis	
The potential risks are based on product labeling for injectable GLP-1R agonists (ie, liraglutide, exenatide and dulaglutide).
 
Pancreatitis has not been observed in the PF-06882961 clinical trial program.
	Per exclusion criteria, potential participants with acute pancreatitis or a history of pancreatitis are not eligible for study entry. Serum amylase and lipase are monitored during the clinical studies.
Hypoglycemia	
Clinical trials with injectable GLP-1R agonists have not demonstrated an increased risk for hypoglycemia. However, when administered in combination with anti-diabetic agents that are known to have an increased risk of hypoglycemia (such as insulin or sulfonylureas), an increased risk for hypoglycemia was observed.
 
Only one adverse event of mild hypoglycemia has been reported in the clinical development program to date.
	Blood glucose is monitored frequently during clinical studies involving patients with T2DM, and hypoglycemia is a well recognized risk in T2DM patients. The IB and ICD inform of the potential increased risk of hypoglycemia when PF-06882961 is administered in combination with anti-diabetic agents that are known to have an increased risk of hypoglycemia (such as insulin or sulfonylureas), which are prohibited in this study.
Impairment in renal function	In rats, minimal renal tubular vacuolation was observed, but this finding was considered to be non-adverse.	Per exclusion criteria, potential participants with significant renal impairment (<60 mL/min/1.73 m ²) are not eligible for study entry. Renal function is monitored at each study

PFIZER CONFIDENTIAL

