14. Previous administration with an investigational drug within 4 months or 5 half-lives preceding the first dose of study intervention used in this study (whichever is longer).
15. Known prior participation in a trial involving PF-06882961.

Diagnostic Assessments:

16. Screening supine BP ≥ 160 mmHg (systolic) or ≥ 100 mmHg (diastolic), following at least 5 minutes of supine rest. BP should be measured in triplicate and the average of the 3 BP values should be used to determine the participant's eligibility.
17. Screening 12-lead ECG that demonstrates clinically relevant abnormalities that may affect participant safety or interpretation of study results (eg, QTcF interval >450 msec, complete LBBB, signs of an acute or indeterminate-age myocardial infarction, ST-T interval changes suggestive of myocardial ischemia, second- or third-degree AV block, or serious bradyarrhythmias or tachyarrhythmias).
 - If QTcF exceeds 450 msec, or QRS exceeds 120 msec, the ECG should be repeated 2 more times and the average of the 3 QTcF or QRS values should be used to determine the participant's eligibility.
18. A positive urine drug test. **Note:** Participants who have been medically prescribed opiates/opioids or benzodiazepines and report the use of these drugs to the investigator at screening (Visit 1) may be allowed to participate with notification to the sponsor.
19. Participants with **ANY** of the following abnormalities in clinical laboratory tests at screening, as assessed by the study-specific laboratory and confirmed by a single repeat test, if deemed necessary:
 - AST **or** ALT level $\geq 2 \times$ ULN;
 - TBili level $\geq 1.5 \times$ ULN; participants with a history of Gilbert's syndrome may have direct bilirubin measured and would be eligible for this study provided the direct bilirubin level is \leq ULN.
 - Fasting C-peptide <0.8 ng/mL.
 - TSH $>1.5 \times$ ULN.
 - Serum calcitonin $>$ ULN.
 - Amylase or lipase $>$ ULN.
 - Fasting blood glucose >270 mg/dL (15.0 mmol/L).

- eGFR <60 mL/min/1.73 m² as calculated by the CKD-EPI equation. ¹⁴

20. FSBG on Day -2 of >270 mg/dL (15.0 mmol/L).

Other Exclusions:

21. History of regular alcohol consumption exceeding 7 drinks/week for female participants or 14 drinks/week for male participants (1 drink = 5 ounces [150 mL] of wine or 12 ounces [360 mL] of beer or 1.5 ounces [45 mL] of hard liquor) within 6 months prior to screening.
22. Known or suspected illicit drug use.

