8.2.5.3. Management of Hyperglycemia

Hyperglycemia is defined as the following:

- Fasting glucose ≥ 270 mg/dL (15.0 mmol/L) using glucometer (or central laboratory).

After randomization, participants noted to have a fasting glucose value (during home glucose monitoring) meeting the above definition of hyperglycemia must be instructed to repeat the measurement the next day (following at least an 8 [preferably 10] hour fast, except water). If the second measurement also meets the above definition, participants must be asked to contact the site and return to the site a day later (following at least an 8 [preferably 10] hour fast, except water) and have blood collected for FPG (and shipped to the central laboratory for analysis).

The investigator should determine if the participant collected the samples after an adequate fasting period; and if the participant is following recommended dietary guidelines. Proper dietary and collected procedures should be reinforced with the participant.

If the results from the central laboratory confirm the readings using glucometer, the participant should be discontinued, and the investigator will recommend further appropriate glycemic treatment according to the local healthcare standards and national guidelines.

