3.1.1.1. Hypoglycemia Monitoring

Hypoglycemia AEs will be recorded in the Case Report Form (CRF) as a separate page. Details of when these will be recorded are given in the protocol Section 8.2.5.2.

For programming purposes, the hypoglycemic AE categories are based on the following:

- Severe Hypoglycemia: Severe is checked in the severity criteria of the CRF. This assessment will be made by the principal investigator based on the protocol definition.
- Documented Symptomatic Hypoglycemia: If (2 – Did the subject have symptoms of hypoglycemia?) Yes and (3 – Was blood glucose measured?) Yes and result <70 mg/dL (3.9 mmol/L) on the CRF, but hypoglycemia is not classified as severe.
- Asymptomatic Hypoglycemia: If (2) No and (3) Yes and result <70 mg/dL (3.9 mmol/L) on the CRF, but hypoglycemia is not classified as severe.
- Probable Symptomatic Hypoglycemia: If (2) Yes and (3) No and (3a – If blood glucose was not measured, did symptoms resolve when treated with carbohydrate or glucagon?) Yes on the CRF, but hypoglycemia is not classified as severe.

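### The measured-glucose limit for severe hypoglycemia gives two different thresholds: 54 mg/dL is 3.0 mmol/L, not 2.7 mmol/L

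*Protocol*

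**What the plan says.** Protocol 8.2.5.2.1 first defines an HAE. The asymptomatic category, for example, needs "a glucose value of <70 mg/dL (3.9 mmol/L) using either glucometer (FSBG) or sponsor-identified central laboratory (plasma glucose"). It then sets three conditions for a severe event, all of which must hold:

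1. The participant could not self-treat because of neurologic impairment and needed another person's help.
2. At least one of the listed neurological symptoms was present.
3. Either measured glucose was at or below "54 mg/dL (2.7 mmol/L) using glucometer (or central laboratory"), or glucose was not measured and the clinical picture reversed with carbohydrate, glucagon or glucose.

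The section closes with the default: "Events that do not meet all the criteria above for severe HAE are characterized as mild or moderate in severity".

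SAP 3.1.1.1 takes the severe category from the severity box on the CRF and adds: "This assessment will be made by the principal investigator based on the protocol definition". Each of the three other categories carries the condition "but hypoglycemia is not classified as severe". SAP 6.1.1.1 lists HAEs and summarizes them by category and treatment.

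**The concern.** The mg/dL and mmol/L figures in criterion 3 are printed as equivalents, but they are different cut-offs. This is an operative rule, because criterion 3 decides the grade whenever criteria 1 and 2 are met and a glucose value exists. An investigator working in mg/dL and one working in mmol/L could grade the same event differently, and both would be following the protocol.

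Nothing in the SAP resolves this, since it restates no limit for severe events and defers to the protocol. In the HAE summary an affected event would appear in either the severe row or the documented symptomatic row. Hypoglycemia is a named potential risk in Protocol 2.3.1, and this rule defines its most serious category. With about 9 participants per arm, one participant moved between rows is 1/9, or about 11%, of an arm.

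**Working it through.** **Inputs**

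| Place | mg/dL | mmol/L printed |
|---|---|---|
| Protocol 8.2.5.2.1, HAE definition; SAP 3.1.1.1 | 70 | 3.9 |
| Protocol 5.2, criteria 19 and 20 (criterion 20: "FSBG on Day -2 of >270 mg/dL (15.0 mmol/L")) | 270 | 15.0 |
| Protocol 8.2.5.3, hyperglycemia ("270 mg/dL (15.0 mmol/L) using glucometer (or central laboratory")) | 270 | 15.0 |
| Protocol 8.2.5.2.1, severe HAE, criterion 3 | 54 | 2.7 |

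**Step 1. Factor implied by each pair** (mg/dL divided by mmol/L)

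- 70 / 3.9 = 17.9
- 270 / 15.0 = 18.0
- 54 / 2.7 = 20.0

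**Step 2. Can rounding explain the difference?** Let each mmol/L figure stand for anything within 0.05 of the printed value.

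- 70/3.9: from 70/3.95 = 17.72 to 70/3.85 = 18.18
- 270/15.0: from 270/15.05 = 17.94 to 270/14.95 = 18.06
- 54/2.7: from 54/2.75 = 19.64 to 54/2.65 = 20.38

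The first two ranges overlap around 18. The third lies wholly above both, so rounding does not account for it.

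**Step 3. Convert with a factor of 18**

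- 54 / 18 = 3.0 mmol/L. The printed 2.7 is not reproduced.
- 2.7 × 18 = 48.6 mg/dL
- Gap: 54 − 48.6 = 5.4 mg/dL, or 3.0 − 2.7 = 0.3 mmol/L

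The answer does not depend on the exact factor. At 17.95 (70/3.9), 54 mg/dL is 3.009 mmol/L; at 18.016 (from the molar mass of glucose), it is 2.997 mmol/L.

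**Step 4. Which readings are affected?** At 18.016:

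| Reading (mg/dL) | mmol/L | At or below 54 mg/dL? | At or below 2.7 mmol/L? |
|---|---|---|---|
| 48 | 2.66 | yes | yes |
| 49 | 2.72 | yes | no (yes if rounded to 2.7) |
| 50 | 2.78 | yes | no |
| 54 | 3.00 | yes | no |

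Six whole-number readings, 49 to 54 mg/dL, are classed differently by the two figures. If mmol/L is read to one decimal, 49 drops out and five remain, 50 to 54.

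**Step 5. Follow an affected event into the SAP.** Take an event that meets criteria 1 and 2 with a measured glucose of 52 mg/dL. By the mg/dL figure all three criteria hold and the severe box is ticked. By the mmol/L figure (52/18 = 2.9) criterion 3 fails and the event is mild or moderate. It then has symptoms and a glucose below 70 mg/dL without being severe, so SAP 3.1.1.1 places it under documented symptomatic hypoglycemia. It counts as one HAE either way.

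**The case against.** The arithmetic is not open to dispute. The case on the other side is that the slip hardly matters, and most of that case stands.

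- **Only a label changes.** HAE status and the repeat-test rule depend on 70 mg/dL. The discontinuation reasons in Protocol 7.1 do not refer to severe HAE, and seriousness is judged separately from severity (Appendix 3). No hypothesis, sample size or power figure uses this limit.
- **Several conditions must coincide.** The participant must be neurologically impaired and unable to self-treat, glucose must have been measured, and the value must fall in a 5.4 mg/dL band. About 27 participants (3 × 9) receive active drug, and insulin and sulfonylureas are prohibited. Protocol 2.3.1 says: "Only one adverse event of mild hypoglycemia has been reported in the clinical development program to date".
- **mg/dL leads.** Every glucose limit gives mg/dL first with mmol/L in parentheses, so most readers would apply 54 mg/dL.
- **The HAE CRF page is not available here.** It may show mg/dL only, the correct conversion, or the same error.
- **Intent is not settled.** The documents do not show whether 54 mg/dL or 2.7 mmol/L was meant.

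These points limit the consequence but do not make the criterion coherent. The convention that mg/dL governs is inferred, not stated, and SAP 3.1.1.1 sends the investigator back to the faulty text. The uncertainty over intent is a reason to ask the sponsor.

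**Conclusion.** The concern holds. Criterion 3 for a severe HAE prints two thresholds as one: 54 mg/dL is 3.0 mmol/L, and 2.7 mmol/L is about 48.6 mg/dL. The difference is 5.4 mg/dL (0.3 mmol/L) and affects six whole-number readings, or five if mmol/L is read to one decimal. This rests only on the protocol's own conversion factor of about 18.

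The likely effect on results is small. Only an event that meets criteria 1 and 2 with a measured glucose in that band changes class, and the only change is from the severe row to the documented symptomatic row. Whether any event would actually be misgraded also depends on the unit the investigator uses and on the wording of the CRF. The correction should still be made, because the error is certain, it sits in a safety classification rule, and it is cheap to put right.

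**What to change.** In Protocol 8.2.5.2.1, criterion 3, change the limit to ≤54 mg/dL (3.0 mmol/L), with mg/dL governing as the leading unit. If the sponsor confirms that 2.7 mmol/L was intended, the mg/dL figure should instead become about 49.

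The SAP needs no change, because it refers to the protocol definition. Check the HAE CRF page and its completion instructions for the same figure. Then check the recorded severity of any HAE with a measured glucose of 49 to 54 mg/dL against the corrected limit.

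The cost is one figure in the protocol text, plus whatever amendment or clarification route the sponsor uses (Appendix 1 describes ethics review of amendments), and a look at what are likely to be very few events, if any.
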